This is a phase 1, open label, single dose study to determine the rates and routes of elimination of a single dose of [¹⁴C]-selumetinib and its metabolites by assessment of concentrations of total [¹⁴C] radioactivity in blood and plasma, concentrations of selumetinib, and N-desmethyl selumetinib in plasma and percent recovery of the radioactive dose in urine and faeces. The study will be conducted at 1 study centre in 6 healthy male volunteers.

Target subject population

Healthy male volunteers, aged 50 to 65 years (inclusive) with regular daily bowel movements.

Investigational product, dosage and mode of administration

Each healthy volunteer will receive a single oral administration of 75 mg (3 x 25 mg) 22.57 MBq (610 µCi) [¹⁴C]-selumetinib.

Comparator, dosage and mode of administration

None

Duration of treatment

Healthy volunteers will receive a single administration of [¹⁴C]-selumetinib on Day 1.

A maximum of 28 days will be allowed for the screening period. Each healthy volunteer will be admitted to the study centre on Day -1 and remain in the study centre up to Day 7. Once the mass balance cumulative recovery >90% has been achieved or <1% of the dose administered has been collected in urine and faeces within 2 consecutive days, healthy volunteers will be permitted to leave the study centre. If emerging data indicates that adequate dose recovery has not been achieved after 7 days then some healthy volunteers may be asked to continue urine and/or faecal collections for a further 3 days either on an inpatient or an outpatient basis, and if adequate dose recovery is still not achieved, some healthy volunteers could be asked to return to the study centre approximately 7 days later, for a further 24 hour collection. For these healthy volunteers, a final follow-up visit will take place on the last day of urine and/or faecal collection.

Outcome variable(s):

- Pharmacokinetics (primary endpoints)

If the data allow, the following parameters will be calculated:

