ALT	Alanine aminotransferase
ARSAC	Administration of Radioactive Substances Advisory Committee
AST	Aspartate aminotransferase
AUC	Area under plasma concentration-time curve from zero extrapolated to infinity
AUC ₍₀₋₁₂₎	Area under plasma concentration-time curve from zero to 12 hours postdose
AUC _(0-t)	Area under plasma concentration-time curve from zero to the last quantifiable concentration
AV	Atrioventricular
BLQ	Below the limit of quantification
BMI	Body mass index
CK	Creatine kinase
CL/F	Apparent plasma clearance
C _{max}	Maximum plasma (peak) drug concentration
C _p	Concentration in plasma
CPA	Clinical Pharmacology Alliance
CPK	Creatine phosphokinase
CRF	Case Report Form (paper)
CRCL	Creatinine clearance
CSA	Clinical Study Agreement
CSP	Clinical Study Protocol
CSR	Clinical Study Report
Cum Ae _f	Cumulative radioactive amount recovered in faeces

Abbreviation or special term	Explanation
Cum Ae _u	Cumulative amount recovered in urine.
Cum fe _f	Cumulative percent (or fraction) of actually administered radioactivity recovered in faeces
Cum fe _u	Cumulative percent (or fraction) of actually administered dose/radioactivity recovered in urine
CV%	Coefficient of variation
C _{wb}	Concentration in whole blood
CYP	Cytochrome P450
DAE	Discontinuation of investigational product due to adverse event
EC	Ethics Committee
ECG	Electrocardiogram
ED	Effective dose
FBE	Free base equivalent
fe _f	Percent (or fraction) of actually administered radioactivity recovered in faeces during each collection interval and overall
fe _u	Percent (or fraction) of actually administered radioactivity recovered in urine during each collection interval and overall
GCP	Good Clinical Practice
GCV	Geometric coefficient of variation
GGT	Gamma glutamyl transpeptidase
GMP	Good Manufacturing Practice
HDPE	High density polyethylene
HIV	Human Immunodeficiency Virus
Ht	Haematocrit
ICF	Informed Consent Form
ICH	International Conference on Harmonisation
IP	Investigational product
LLOQ	Lower limit of quantification
LSC	Liquid scintillation counting
LSLV	Last Subject Last Visit
LVEF	Left ventricular ejection fraction
max	Maximum
MCH	Mean cell haemoglobin

Abbreviation or special term	Explanation
MCHC	Mean cell haemoglobin concentration
MCV	Mean cell volume
MedDRA	Medical Dictionary for Regulatory Activities
MEK	Mitogen activated protein kinase
min	Minimum
MR _{AUC}	Metabolite to selumetinib AUC ratio
MR _{C_{max}}	Metabolite to selumetinib C _{max} ratio
MRT	Mean residence time

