5.5.2 Doses and treatment regimens

Each healthy volunteer will receive 3 x 25 mg [¹⁴C]-selumetinib Hyd-Sulfate oral capsules (FBE) as a single dose on Day 1. Healthy volunteers should be fasted from 10 hours prior to IP administration and remain fasted for 4 hours after administration. No fluids will be allowed from 1 hour prior to IP administration until 1 hour after IP administration, except the water needed (240 mL) to consume the IP. Thereafter, healthy volunteers will be allowed to have free access to water.

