11.3 Calculation or derivation of patient reported outcome variables (Not applicable)

11.4 Calculation or derivation of pharmacokinetic variables

The PK analyses of [¹⁴C] radioactivity concentration data in whole blood, plasma, urine, and faeces and selumetinib and N-desmethyl selumetinib concentration data in plasma will be performed at . Pharmacokinetic analyses will be conducted according to Standard Operating Procedures unless otherwise specified.

Total [¹⁴C] radioactivity in whole blood and plasma will be converted to concentration equivalents of selumetinib based on the actual specific activity of the dose.

Pharmacokinetic parameters will be determined using standard noncompartmental methods with WinNonlin[®] Professional Version 5.2 or higher

or SAS[®] Version 9.2 or higher

Actual elapsed time from dosing will be used for final blood-based

PK parameter calculations. Pharmacokinetic parameter units will be consistent with the concentration units specified in the bioanalytical data.

The following PK parameters will be determined for plasma selumetinib and N-desmethyl selumetinib and whole blood and plasma [¹⁴C] radioactivity:

AUC	Area under the concentration-time curve in the sampled matrix from time zero to infinity, calculated by linear up/log down trapezoidal summation
AUC _(0-t)	Area under the concentration-time curve in the sampled matrix from time zero to the time of the last quantifiable concentration, calculated by linear up/log down trapezoidal summation
AUC ₍₀₋₁₂₎	Area under the concentration-time curve in the sampled matrix from time zero to the time of 12 hours, calculated by linear up/log down trapezoidal summation
C _{max}	Maximum concentration in the sampled matrix, obtained directly from the observed concentration versus time data
t _{max}	Time to C _{max}
CL/F	Apparent oral plasma clearance (selumetinib only, whole blood and plasma radioactivity only)
V _{ss} /F	Apparent volume at distribution equilibrium, mean residence time (MRT)*CL/F (selumetinib only, whole blood and plasma radioactivity only)
V _z /F	Apparent volume at distribution (selumetinib only, whole blood and plasma radioactivity only)
t _{1/2}	Terminal half-life
λ _z	Terminal rate constant
MR _{AUC}	AUC metabolite to parent ratio, N-desmethyl selumetinib AUC/selumetinib AUC

$MR_{C_{max}}$	C_{max} metabolite to parent ratio, N-desmethyl selumetinib $C_{max}/\text{selumetinib } C_{max}$

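### Vss/F is defined as MRT × CL/F after oral dosing only, so it carries absorption time and overstates the steady-state volume

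*Protocol*

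**What the plan says.** Section 11.4 gives the formula for Vss/F outright: "Apparent volume at distribution equilibrium, mean residence time (MRT)*CL/F". It applies to three analytes, plasma selumetinib and total radioactivity in whole blood and in plasma ("selumetinib only, whole blood and plasma radioactivity only"). Vz/F and CL/F are reported for the same three. The estimation method is stated there too: "Pharmacokinetic parameters will be determined using standard noncompartmental methods".

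On dosing, the synopsis says "Each healthy volunteer will receive a single oral administration of 75 mg" and "Healthy volunteers will receive a single administration of [¹⁴C]-selumetinib on Day 1". Section 5.5.2 confirms the form: "Each healthy volunteer will receive 3 x 25 mg [¹⁴C]-selumetinib Hyd-Sulfate oral capsules (FBE) as a single dose on Day 1". No intravenous dose is planned.

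The abbreviation list expands MRT only as "Mean residence time" and reads Vss/F as the distribution volume at steady state. Nothing in the protocol subtracts an absorption time or says that one is included. The synopsis names Vss/F for selumetinib and for radioactivity, under the heading for the primary pharmacokinetic endpoints.

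**The concern.** The identity Vss = CL × MRT holds for the residence time of drug already in the circulation, that is, the disposition MRT. A noncompartmental MRT from an oral profile also counts the time that drug spends waiting to be absorbed. Put into the Section 11.4 formula, it yields a volume that is too large and that moves with absorption rate and elimination as well as with distribution.

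At stake is one descriptive parameter that the protocol presents as a steady-state volume. Because the error lies in the definition, it passes straight into every individual value and every summary statistic. With no intravenous arm it cannot be removed afterwards. The planned diagnostics (Rsq and extrapolated AUC percentage) check the terminal fit and the extrapolated area, so they would not reveal it. A report could also show Vss/F above Vz/F for the same volunteer with nothing to explain why.

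**Working it through.** The protocol states no figure for this point, so there is none to reproduce. The check has an algebraic step and two illustrative models.

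**Inputs from the protocol.** Vss/F = MRT × CL/F (Section 11.4); single oral capsule dose (synopsis, Section 5.5.2); noncompartmental analysis with linear up/log down trapezoids (Section 11.4); 19 blood sampling times from 0 to 168 h (Table 3).

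**Inputs assumed, because the protocol gives none.** Absorption rate constant ka, half-life and distribution rate constants.

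**Algebra.** After an oral dose, with AUMC the area under the first-moment curve:

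- MRT(oral) = AUMC/AUC = MRT(disposition) + MAT
- MRT(oral) × CL/F = Vss/F + MAT × CL/F
- Since Vss/F = MRT(disposition) × CL/F, relative bias = MAT / MRT(disposition)

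MAT is above zero for a capsule, so the bias is upward in every profile.

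**One compartment, first-order absorption.** Here MRT(disposition) = 1/k, MAT = 1/ka and true Vss equals Vz. So (MRT × CL/F)/(Vz/F) = 1 + k/ka, with k = 0.693/half-life:

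| Half-life | k (per h) | ka 0.7 | ka 1 | ka 2 |
|---|---|---|---|---|
| 5 h | 0.1386 | 1.198 | 1.139 | 1.069 |
| 8 h | 0.0866 | 1.124 | 1.087 | 1.043 |

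The overstatement is about 4% to 20%. Widening the assumptions to half-life 3 to 14 h and ka 0.3 to 4 per h (20 combinations) gives an analytic ratio of 1.01 to 1.77. For example, it is 1.12 at 6 h and ka 1 per h, and 1.46 at 3 h and ka 0.5 per h.

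Noise-free profiles were also simulated at the Table 3 times, dropping values below 0.1% of the peak and taking λz from the last three points. The ratio of computed Vss/F to computed Vz/F was 1.02 to 1.48, above 1 in all 20. The top of the range is lower than the analytic one because λz, and so Vz/F, is itself distorted when ka is close to k.

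**Two compartments.** Four sets of rate constants were crossed with ka of 0.3, 0.5, 1 and 2 per h, giving 16 scenarios with central volume set to 1. The formula overstated true Vss in all 16, by 5% to 70%. It exceeded true Vz in 3. Two worked cases:

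- k10 0.2, k12 0.05, k21 0.3, ka 0.5 per h. True Vss = 1 + 0.05/0.3 = 1.167. Added term = 0.2 × (1/0.5) = 0.4, so the formula gives 1.567 (+34%). The terminal rate is 0.15 per h, so Vz = 0.2/0.15 = 1.333. The computed value exceeds Vz.
- k10 0.3, k12 0.2, k21 0.1, ka 1 per h. True Vss = 1 + 0.2/0.1 = 3.0. Added term = 0.3 × 1 = 0.3, so the formula gives 3.3 (+10%). Vz is 5.449. The value is inflated but stays below Vz.

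All three exceedances came from the set with the small peripheral compartment, at ka of 1 per h or less.

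**The case against.** The strongest reply is that little depends on this parameter. The primary objective is rates and routes of excretion, there are six volunteers, the analysis is descriptive, and Vss/F enters no ratio, release criterion or decision rule. The formula is stated openly and the parameter is called apparent, so a reader can see what is computed. The synopsis also makes the calculation conditional on the data. The point about limited impact stands. The rest does not rescue the definition. Dividing by F allows for the fraction absorbed, not for the time absorption takes, and the conditional wording leaves the formula unchanged.

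The objection also rightly blocks some stronger readings:

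- A reader might infer that reported Vss/F will exceed Vz/F and so be impossible. The one-compartment model forces this, because true Vss equals Vz there. With two compartments it happened in 3 of 16 scenarios. The ordering of the true volumes also needs linear disposition without marked recirculation. Section 1.1 reports biliary excretion in rats and glucuronidation as a dominant human route, so recirculation cannot be ruled out from the document.
- A reader might take 4% to 20% as the bias in this trial. It rests on assumed values of ka and half-life.
- A reader might conclude that Vss/F is uniquely meaningless for total radioactivity. Vz/F and CL/F for total radioactivity are also composites of parent and metabolites, so that argument cannot single out Vss/F.

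**Conclusion.** The definition is wrong as written for oral-only data: it returns Vss/F + MAT × CL/F and overstates the steady-state volume in every profile. This follows from the stated formula, route and method, and needs no assumed number. It may exceed Vz/F but need not.

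The size is MAT divided by disposition MRT and cannot be fixed from the protocol. The illustrative one-compartment range is about 4% to 20% for half-life 5 to 8 h and ka 0.7 to 2 per h, and larger with slower absorption or a shorter half-life. The consequence is confined to this one parameter. Recovery, AUC, Cmax, half-life, CL/F and Vz/F are calculated without it. It is worth correcting because the parameter is named among the synopsis outcomes and the correction is only wording; it does not threaten the study's main results.

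**What to change.** In the synopsis and Section 11.4, do one of the following for selumetinib:

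- drop Vss/F; or
- report MRT as oral MRT (disposition MRT plus MAT), and label MRT × CL/F as an upper bound on Vss/F that includes absorption time. Align the abbreviation list with that label.

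For whole-blood and plasma total radioactivity, drop Vss/F or apply the same label. Add one sentence saying that all apparent volumes and clearances of total radioactivity, Vz/F and CL/F included, are composites of parent and metabolites.

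The cost is wording, and one descriptive parameter fewer or more cautiously labelled. Sampling, dosing and conduct do not change, and no other planned parameter depends on Vss/F.

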N	Number of data points included in the log-linear regression analysis used to determine λ_z (a minimum of 3 data points will be used for λ_z determination)
NA	Not applicable
ND	Not determined
OAE	Other significant adverse event (see definition in Section 11.2.1)
PCV	Packed cell volume
PK	Pharmacokinetic
PL	Plasma selumetinib or plasma N-desmethyl selumetinib
PR	Plasma radioactivity
QT	ECG interval measured from beginning of Q wave (or the R wave if Q is missing) to the end of the T wave; the time interval of ventricular depolarisation and repolarisation.
QTc	Corrected QT interval
QTcF	QT interval corrected according to Fridericia's formula
RBC	Red blood cells
Rsq	Goodness of fit statistic for calculation of λ_z (regression coefficient)
SAE	Serious adverse event (see definition in Section 6.4.2).
SD	Standard deviation
SI	Système International
SOP	Standard operating procedure
t _½	Half-life
t _{max}	Time to C _{max}
ULN	Upper limits of normal
V _{ss} /F	Volume of distribution at steady state
V _z /F	Apparent volume of distribution

Abbreviation or special term	Explanation
wb	Whole blood
WBC	White blood cell
WBR	Whole blood radioactivity

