$C_{max}(\text{PL})/C_{max}(\text{PR})$	C_{max} ratio of plasma selumetinib or N-desmethyl selumetinib (PL) to plasma radioactivity (PR)
$C_{max}(\text{WBR})/C_{max}(\text{PR})$	C_{max} ratio of whole blood radioactivity (WBR) to PR
$\text{AUC}(\text{PL})/\text{AUC}(\text{PR})$	AUC ratio of PL to (PR)
$\text{AUC}(\text{WBR})/\text{AUC}(\text{PR})$	AUC ratio of WBR to PR

The following PK parameters for plasma selumetinib and N-desmethyl selumetinib and whole blood and plasma [^{14}C] radioactivity will be calculated for diagnostic purposes and listed, but will not be summarised:

$t_{1/2}$, Interval	The time interval of the log-linear regress to determine $t_{1/2}$
N	Number of data points included in the log-linear regression analysis used to determine λ_z (a minimum of 3 data points will be used for λ_z determination)
Rsq	Coefficient of determination for calculation of λ_z (λ_z and related parameters will be reported only if Rsq is 0.800 or more)
%AUC _{ex}	Percentage of AUC obtained by extrapolation (if the extrapolated area is greater than 20% then AUC for that specific profile will not be reported)

The ratio of plasma selumetinib to plasma radioactivity concentrations, N-desmethyl selumetinib concentrations to plasma radioactivity concentrations, and whole blood to plasma [^{14}C] radioactivity concentrations and the distribution of radioactivity in blood cells (expressed as percentage) will be reported for each sampling time to assess the radioactivity distribution in blood based matrices over time. The distribution of radioactivity in red blood cells will be calculated by the following equation:

$$\frac{C_{wb} - (1 - Ht) \times C_p}{C_{wb}} \times 100\%$$

where C_{wb} is concentration in whole blood, C_p is concentration in plasma and H_t is haematocrit [H_t will be the mean value of the laboratory H_t data obtained from Day -1 and follow-up].

The following PK parameters will be computed from the urine total radioactivity:

Ae_u	Amount recovered in urine during each collection interval (t_1 to t_2), calculated as urine concentration or concentration equivalent x urine volume
Cum Ae_u	Cumulative amount recovered in urine
fe_u	Percent (or fraction) of actually administered dose/radioactivity recovered in urine during each collection interval and overall
Cum fe_u	Cumulative percent (or fraction) of actually administered dose/radioactivity recovered in urine

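### The 20% extrapolation rule in Section 11.4 withholds AUC but not the clearance, volumes and ratios built on that AUC

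*Protocol*

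**What the plan says.** Section 11.4 lists the blood-based parameters to be determined. They include AUC to infinity, CL/F, Vz/F, Vss/F (given as "Apparent volume at distribution equilibrium, mean residence time (MRT)*CL/F"), the metabolite-to-parent ratio MR_AUC, and the ratios AUC(PL)/AUC(PR) and AUC(WBR)/AUC(PR). Section 12.2.2 has the blood-based parameters summarised with descriptive statistics.

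Among the diagnostics, Section 11.4 then sets two acceptance rules:

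- **Fit.** λ_z and "related parameters will be reported only if Rsq is 0.800 or more", where "a minimum of 3 data points will be used for λ_z determination".
- **Extrapolation.** "if the extrapolated area is greater than 20% then AUC for that specific profile will not be reported".

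The fit interval, the number of points, Rsq and the extrapolated percentage are to be listed for each profile.

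**The concern.** The two rules sit side by side and differ in reach. The fit rule extends to dependent parameters, while the extrapolation rule names only AUC. Nothing else in the protocol removes the quantities computed from a rejected AUC, so the general instruction to determine and summarise them still applies.

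Secondary objective 2 is the calculation of these parameters, and the synopsis also places them under the pharmacokinetic primary endpoints. With six volunteers and no replacement of withdrawals (Section 5.9), a single profile carries visible weight in a mean, SD or geometric CV. Two programmers could also follow the same sentence and produce different tables, one dropping CL/F with the AUC and one keeping it.

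**Working it through.** The plan gives thresholds but no computed figure here, so there is nothing to reproduce. The check is which parameters depend on the rejected AUC, and how far they can move.

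**1. Dependence on AUC.** Vss/F, MR_AUC and the ratios are defined in Section 11.4. The other formulas are the standard noncompartmental ones.

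| Parameter | Formula | Uses AUC | Named in the 20% rule |
|---|---|---|---|
| AUC | – | – | yes |
| CL/F | Dose / AUC | yes | no |
| Vz/F | Dose / (λ_z × AUC) | yes | no |
| Vss/F | MRT × CL/F, with MRT = AUMC / AUC | yes, twice | no |
| MR_AUC | AUC metabolite / AUC parent | yes | no |
| AUC(PL)/AUC(PR) | ratio of two AUCs | yes | no |
| AUC(WBR)/AUC(PR) | ratio of two AUCs | yes | no |

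Since CL/F = Dose/AUC, AUC = 75 mg / (CL/F), so a printed CL/F discloses the withheld AUC. A ratio draws on two profiles, and a rule about one specific profile does not say what happens when only one of the two AUCs fails.

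**2. Illustrative size.** Assume a mono-exponential profile with true extrapolated share f, and λ_z estimated at k times its true value. Set the true AUC to 1. Then:

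- estimated AUC = (1 − f) + f/k
- apparent extrapolated share = (f/k) / estimated AUC
- CL/F relative to truth = 1 / estimated AUC
- Vz/F relative to truth = 1 / (k × estimated AUC)

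For f = 0.20 and k = 0.5: estimated AUC = 0.80 + 0.40 = 1.20; apparent share = 0.40/1.20 = 33.3%; CL/F = 0.833; Vz/F = 1.667.

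Cases with an apparent share above 20%, where AUC is withheld:

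| f | k | Apparent share | CL/F ratio | Vz/F ratio |
|---|---|---|---|---|
| 0.20 | 0.5 | 33.3% | 0.833 | 1.667 |
| 0.30 | 0.5 | 46.2% | 0.769 | 1.538 |
| 0.40 | 0.5 | 57.1% | 0.714 | 1.429 |
| 0.30 | 1.5 | 22.2% | 1.111 | 0.741 |
| 0.40 | 2 | 25.0% | 1.250 | 0.625 |

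**3. Effect on an n = 6 summary.** Take five identical correct values and one from the first row.

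- Vz/F: the arithmetic mean rises by 0.667/6 = 11.1%. On the log scale s² = (ln 1.667)²/6 = 0.0435, so GCV% = 100 × √(exp(0.0435) − 1) = 21.1%, where it would otherwise be 0.
- CL/F: the mean falls by 0.167/6 = 2.8%. Here s² = (ln 0.833)²/6 = 0.00554, so GCV% = 7.5%.

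**4. The fit rule, for the optional suggestions only.** With t = √(Rsq(N − 2)/(1 − Rsq)) on N − 2 df, Rsq = 0.800 gives:

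| N | t | p | 95% interval for λ_z, as a multiple of the estimate |
|---|---|---|---|
| 3 | 2.00 | 0.295 | −5.35 to 7.35 |
| 4 | 2.83 | 0.106 | −0.52 to 2.52 |
| 5 | 3.46 | 0.041 | 0.08 to 1.92 |

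Adjusted Rsq = 1 − (1 − Rsq)(N − 1)/(N − 2). Requiring 0.80 of it means Rsq 0.90 at N = 3 (p = 0.205) and 0.867 at N = 4 (p = 0.069).

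**The case against.** The text is silent on the derived parameters; it does not say that they are reported when AUC is not. Because dose/(CL/F) returns the AUC, the literal reading is unlikely to be what the authors want. The synopsis makes calculation conditional on adequate data, and Section 11.4 defers to SOPs that are not shown. A SAP may close the gap, and each profile's diagnostics are listed, so a weak value can be seen.

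Part of this stands. The defect is an omission in a rule, not an instruction to publish bad values, and the listings limit the harm. But the SOPs govern only where the protocol does not specify otherwise, and here it does specify. The synopsis proviso sets no criterion. Listing the diagnostics does not take a value out of the summary statistics.

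A reader might go further and infer that the Rsq limit itself is wrong. The documents do not support that. Three points is a minimum, the study is descriptive, and from five points 0.800 already excludes a zero slope. Moving the limit to adjusted Rsq would still leave zero inside the interval at three and four points and would tighten the rule at five. That is a choice between conventional cut-offs.

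A reader might also infer that the 20% limit fails to protect Vss/F, because 20% of AUC extrapolated corresponds to 0.2 × (1 − ln 0.2) = 52% of AUMC. That figure needs a profile that is mono-exponential from time zero. For an oral dose it is only illustrative.

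**Conclusion.** The point holds for the extrapolation rule. As written, CL/F, Vz/F, Vss/F, MR_AUC and the two AUC ratios remain in the summaries although the AUC beneath them has been rejected.

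The size is moderate and depends on assumptions about profile shape and λ_z error, because the documents give no human half-life or assay error. In the rejected profiles computed with a two-fold λ_z error, CL/F was 17% to 29% low or 25% high, and Vz/F was 43% to 67% high or 37.5% low. For profiles that pass the 20% limit, the same error moved CL/F by only 5% to 18%, so it would be too strong to say that CL/F is generally unreliable under this plan.

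It would also be too strong to read this as a threat to the mass balance result. Urine and faecal recovery use neither λ_z nor AUC.

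**What to change.** Reword the extrapolation rule in Section 11.4, for example: *For any profile with more than 20% of AUC extrapolated, AUC, CL/F, Vz/F, MRT and Vss/F, and any MR_AUC, AUC(PL)/AUC(PR) or AUC(WBR)/AUC(PR) that uses that AUC as numerator or denominator, will be listed with a flag and excluded from the summary statistics.*

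This changes one sentence and needs no change to sampling or assays. The downside is that a few profiles may contribute no value, so n should be shown beside each summary. Section 12.2.2 already gives n as an example statistic.

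Optional:

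- Flag half-lives from three- or four-point fits, or use adjusted Rsq, accepting that the latter is only a partial remedy.
- Reconcile the two descriptions of Rsq. The abbreviation list labels it a regression coefficient, while Section 11.4 has "Coefficient of determination for calculation of λ_z". If 0.800 were applied to r, the Rsq limit would be 0.8² = 0.64 (p = 0.41 at N = 3).
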